2.2. Secondary Objectives

The secondary objectives of the study are:

- To evaluate subject demographics and leukemic blast characteristics and their correlation with response to lenalidomide.
- To further evaluate lenalidomide activity with regards to response assessment outcome rates, transplantation rate, duration of response (DoR) and durable response rate.
- To evaluate the safety of lenalidomide including rates of graft-versus-host disease (GVHD) flare and reactivation.
- To determine the pharmacokinetics (PK) of lenalidomide in plasma.

[REDACTED]

3. STUDY ENDPOINTS

3.1. Primary Endpoint

- Morphologic complete response rate (CR or CRi) within the first 4 cycles of treatment with lenalidomide.

3.2. Secondary Endpoints

- Durable response rate.
- Duration of response (DoR).
- Disease assessment outcomes and overall response rate (ORR).
- Rate of hematopoietic stem cell transplant (HSCT).
- Incidence and severity of treatment-emergent adverse events (TEAEs).
- Rates of acute and chronic graft-versus-host disease (GVHD).
- Plasma pharmacokinetic (PK) parameters including lenalidomide apparent clearance and volume of distribution.
- Correlation of peripheral white blood cell count, absolute blast count and cytogenetics with response to lenalidomide.

[REDACTED]

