10.6.2. Secondary endpoints

Overall Response Rate

Overall response rate defined as the proportion of subjects with CR, CRi or PR among all subjects evaluable for ORR assessment. The ORR rate at the end of Cycles 1, 2, 3, 4, 8 and 12 will be categorized, and the rate will be calculated by dividing the number of subjects completing each given cycle of interest. The corresponding Clopper Pearson 95% confidence interval will be calculated for the response rate at the end of each pre-specified cycle.

Disease Assessment Outcome

Disease assessment outcome at the end of Cycles 1, 2, 3, 4, 8 and 12 of lenalidomide administered shall be categorized according to the Cheson criteria (Cheson, 2003). The response rate for each of the best response criteria will be calculated as the total number of subjects in a given category at each time point over the number of subjects completing each corresponding cycle. The corresponding Clopper Pearson 95% confidence interval will be calculated per response category at the end of each pre-specified cycle.

Durable Response Rate

Durable response rate is defined as the proportion of subjects achieving a bone marrow confirmed CR/CRi lasting at least 3 months or until transplantation if earlier among all subjects evaluable for the durable response rate assessment. The corresponding Clopper Pearson 95% confidence interval will be calculated for the durable response rate.

Duration of Response

Duration of response is defined as the time from date of the first observed response (CR, CRi or PR) until morphologic relapse, molecular/cytogenetic relapse, or death only for subjects achieving a response. Subjects alive and leukemia-free at the time of the statistical analysis will be censored at the time of their last disease assessment. The median DoR time along with the corresponding 95% confidence interval based on Greenwood's standard error will be calculated using Kaplan-Meier methods. The proportion of subjects remaining without a DoR event at 6, 12 and 24 months will also be presented. Should the number of subjects considered for inclusion in DoR analysis fall below a third of the total sample size, the DoR shall be analyzed descriptively due to the low number of subjects available for analysis. Duration of response shall be analyzed both allowing for censoring of subjects at time of HSCT and without censoring of subjects at the time of HSCT.

Transplantation Rate

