3.2. Secondary Objectives

The secondary objectives of the study are:

- To evaluate subject demographics and leukemic blast characteristics and their correlation with response to lenalidomide.
- To further evaluate lenalidomide activity with regards to response assessment outcome rates, transplantation rate and durable response rate.
- To evaluate the safety of lenalidomide including rates of graft-versus-host disease (GVHD) flare and reactivation.
- To determine the pharmacokinetics (PK) of lenalidomide in plasma.

[REDACTED]

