4.2.2. Secondary Endpoints

The secondary endpoints of the study are the following:

- Time to response.
- Durable response rate based on the revised AML IWG Criteria ([Cheson, 2003](#), see Section 18.1).
- Disease assessment outcomes and overall response rate (ORR).
- Rate of hematopoietic stem cell transplant (HSCT).
- Incidence and severity of treatment-emergent adverse events (TEAEs).
- Rates of acute and chronic graft-versus-host disease (GVHD).
- Plasma pharmacokinetic (PK) parameters including lenalidomide apparent clearance and volume of distribution.
- Correlation of peripheral white blood cell count, absolute blast count and cytogenetics with response to lenalidomide.

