15. PRIMARY AND END OF STUDY FINAL ANALYSES

All tables, listings and figures detailed in this SAP will be provided for the primary final analysis that will be conducted when all on treatment subjects will have completed their Cycle 4 Day 28 assessments or will have met discontinuation criteria, whichever occurs first.

For the end of study final analysis, all outputs will be rerun once all subjects will have discontinued the follow-up period (up to 5 years after the last subject first dose of lenalidomide).

16. Changes to the Statistical Analyses Section of the Protocol

Denominator of the ORR rate will be defined as the number of subjects starting the cycle of interest instead of the number of subjects completing the cycle of interest as stated in the protocol.

Correlation will be computed between response and laboratory results obtained at baseline, instead of correlation between response and laboratory results at diagnosis and relapse as stated in the protocol.

The IWG response criteria in this study was brought in line with the actual criteria, ie. 'Progressive Disease' was replaced with 'Treatment Failure'.

Time to response endpoint was added as a secondary endpoint.

During the course of the study, due to a low (1 or fewer) number of subjects reporting certain measurements or to redundant presentation, it was determined that the analyses listed below would not be conducted:

- Summaries of prior cancer history, prior procedures/surgeries, procedures for prior cancers not under study and radiation treatment for prior cancers not under study.
- [REDACTED]
- Correlation between response with baseline/screening peripheral white blood cell count, absolute blast count, cytogenetics, [REDACTED]
- [REDACTED]
- Summary of durable response rate.
- AE summary tables for (treatment-emergent adverse events leading to death, SAEs related to lenalidomide, SAEs leading to discontinuation, Grade $\frac{3}{4}$ TEAEs by maximum intensity.
- Summary for AE of special interest related to lenalidomide, SAEs of special interest related to lenalidomide or leading to discontinuation of lenalidomide. AEs of special interest by maximum intensity.
- Second primary malignancy related tables, listings and figures.
- [REDACTED]
- Population PK analysis.

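### Duration of response, a protocol secondary endpoint with a defined analysis, is not carried into the SAP, and no legible SAP text declares the omission

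*Protocol*

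**What the plan says.** **Protocol.** Section 2.2 sets a secondary objective that covers "transplantation rate, duration of response (DoR) and durable response rate", and section 3.2 lists "Duration of response (DoR" as an endpoint. Section 10.6.2 gives the analysis:

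- The clock starts at the first CR, CRi or PR and stops at morphologic, molecular or cytogenetic relapse, or death.
- Subjects alive and leukemia-free are censored at their last disease assessment.
- The outputs are a Kaplan-Meier median with 95% CI and event-free proportions at 6, 12 and 24 months.
- The analysis is run with and without censoring at HSCT.
- A small-number rule applies: "Should the number of subjects considered for inclusion in DoR analysis fall below a third of the total sample size", the analysis becomes descriptive.

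**SAP.** Section 3.2 states the matching objective as "To further evaluate lenalidomide activity with regards to response assessment outcome rates, transplantation rate and durable response rate", without duration of response. Section 4.2.2 opens "The secondary endpoints of the study are the following" and begins its list with "Time to response"; duration of response is not in it. Sections 10.2.1 to 10.2.6 cover time to response, overall response rate, disease assessment outcome, durable response rate, transplantation rate and correlates of response. Section 16 declares "Time to response endpoint was added as a secondary endpoint" and, among analyses not to be conducted, "Summary of durable response rate". It has no legible entry on duration of response.

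**The concern.** The SAP is the document that gets programmed. An endpoint missing from its objectives, endpoints and analysis sections yields no table unless someone goes back to the protocol. Here a stated secondary objective would be left without an estimate, and a reader of SAP 16 would not learn that anything differed from the protocol. The nearest substitute, the durable response rate summary, is also cancelled in SAP 16. How long a response lasts matters in a single-arm leukemia trial whose primary endpoint counts a CR/CRi seen at any point in four cycles, even if it is lost before the end of Cycle 4.

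**Working it through.** **1. The two documents side by side**

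| Item | Protocol | SAP |
|---|---|---|
| Secondary objective | 2.2: included | 3.2: same objective, without it |
| Secondary endpoint | 3.2: included | 4.2.2: absent; no blacked-out item in the list |
| Analysis | 10.6.2: defined | 10.2.1 to 10.2.6: consecutive numbering, none |
| Abbreviation | defined in the text | section 1: no entry, and no blacked-out row where it would fall (between DMC and eCRF) |
| Declared as a change | not applicable | 16: nothing legible |

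**2. Likely cause**

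The protocol's amendment history, used here only as history, says that one amendment added duration of response, cut the number of sites from 75 to 70, and reworded the first DMC review to include subjects who had discontinued. Protocol 4.1 now has about 70 sites and the reworded review. SAP 4.1 still has about 75 sites and a review after 4 subjects have completed a cycle, without the discontinuation clause. Text from before that amendment therefore survives in the SAP.

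**3. What the SAP still delivers**

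SAP 10 provides listings for all endpoints. SAP 10.1 lists the response assessment page. SAP 10.2.3 tabulates outcomes at Cycles 1, 2, 3, 4, 8 and 12, including relapse after CR or CRi. SAP 10.2.5 lists transplant data. None of these derives a duration or a censoring status.

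**4. The one-third rule (secondary note)**

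Inputs from Protocol 10.3: 18 + 25 = 43 subjects, CR/CRi rates of 10% and 25%, continue with at least 3 of 18, activity with at least 8 of 43.

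The plan's own design reproduces. P(declare activity) = Σ over x = 3 to 18 of Bin(x; 18, p) × P(Bin(25, p) ≥ 8 − x). This gives 0.0480 at p = 0.10 and 0.8003 at p = 0.25, within the stated 5% and 80%.

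Threshold: 43 / 3 = 14.33, so 15 responders are needed. With a denominator of 47, 47 / 3 = 15.67, so 16. The protocol does not say which total applies.

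Expected CR/CRi at the target: 43 × 0.25 = 10.75, below 15.

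If every responder is a CR/CRi, P(Bin(43, 0.25) ≥ 15) = 0.0962. Requiring at least 3 of 18 in Stage 1 gives 0.0958. But the endpoint also counts PR, for which the documents give no rate. With a PR rate q on top of 25% CR/CRi, x the CR/CRi count and y the PR count in Stage 1:

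P = Σ over x ≥ 3 and y of P(x, y among 18) × P(Bin(25, 0.25 + q) ≥ 15 − x − y)

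| Assumed PR rate (percentage points) | P(at least 15 of 43) | P(at least 16 of 47) |
|---|---|---|
| 0 | 0.0958 | 0.1050 |
| 1 | 0.1248 | 0.1372 |
| 2 | 0.1586 | 0.1745 |
| 5 | 0.2849 | 0.3124 |
| 10 | 0.5305 | 0.5681 |
| 15 | 0.7240 | 0.7525 |

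The 47 column assumes that all 47 can respond. Among trials that reach Stage 2 (probability 0.8647), the 43-subject figures are 0.0958 / 0.8647 = 0.111 with no PR, 0.2849 / 0.8647 = 0.329 with 5 points and 0.5305 / 0.8647 = 0.614 with 10.

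**The case against.** **Redaction.** Several bullets in SAP 16 and the block between SAP 11.8 and 13 are blacked out, and SAP 18.3 mentions a survival analysis and endpoint-specific censoring that no legible section contains. Time-to-event content may sit in hidden text. This limits the claim to what is legible. It does not make duration of response a secondary endpoint of the SAP, because the objective and the endpoint list are visible and complete without it.

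**Little is lost.** SAP 16 justifies its cancelled analyses by counts of 1 or fewer or by redundancy. With so few responders a Kaplan-Meier curve would say nothing. That stands, but it argues for a listing or a one-line declaration, and neither is legible.

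**The durable response summary.** Its cancellation is openly declared and it is a different endpoint. It is context here, not a second undeclared loss.

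**Stronger readings that the documents do not support.**

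- A reader might infer that the endpoint was deliberately removed. The surviving pre-amendment text points instead to an incomplete update.
- A reader might infer that nothing on persistence of response will be reported. The by-cycle outcomes and listings say otherwise.
- A reader might infer that the one-third rule would block Kaplan-Meier output in more than 90% of trials at the target. That applies a CR/CRi target to an endpoint that counts PR and has no four-cycle limit; one point of PR already lifts the chance of output above 12%.
- A reader might infer that the descriptive fallback ignores censoring. Protocol 10.6.2 sets censoring rules in the same paragraph and leaves the form of the description open. A prespecified small-number fallback is a defensible choice, so deleting it is a matter of preference.

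**Conclusion.** The point stands as a mismatch between the documents: a protocol secondary objective and endpoint with a defined analysis has no counterpart in the legible SAP, and no legible line declares this. The effect is one secondary endpoint without a planned estimate. The stage decisions and the primary analysis are untouched. It should be corrected.

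The one-third rule is a note only. At the 25% CR/CRi target, whether Kaplan-Meier output appears depends on the PR rate: about 10% with none, 28% with 5 points and 53% with 10. These figures assume 43 subjects, independent responses, and no first responses after Cycle 4. Later responses or a higher CR/CRi rate would raise them. A trial with 8 to 14 CR/CRi and no PR would meet the activity criterion and still fall into the descriptive branch.

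**What to change.** Add duration of response to SAP 3.2 and 4.2.2, and write a new subsection of SAP 10.2 that follows Protocol 10.6.2: CR/CRi/PR responders, the protocol's events, censoring at last disease assessment, Kaplan-Meier median with 95% CI, the 6, 12 and 24 month proportions, and versions with and without censoring at HSCT. Add a per-responder listing of duration and censoring status, produced whatever the number of responders. If the one-third rule is kept, state its denominator and what the descriptive output contains when some durations are censored.

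If the endpoint is dropped on purpose, say so in SAP 16 and give the reason.

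The cost is SAP wording, one table and one listing. The response assessment and transplant data that the SAP already lists are the main inputs.

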4. OVERALL STUDY DESIGN

4.1. Study Design

This is a multicenter, open-label, single-arm, Phase 2, Simon's Optimal two-stage design study, with an Optional Extension Phase (OEP), that will assess the activity, safety and PK of lenalidomide in pediatric subjects from 1 to ≤ 18 years of age with second or greater rAML. A total of 43 evaluable subjects (18 subjects in Stage 1 and an additional 25 subjects in Stage 2) are required for assessment of the primary endpoint. To allow for subjects found to be unevaluable for the primary endpoint due to an incorrect diagnosis, not having a disease assessment post screening, or who discontinued prior to receiving lenalidomide, up to 4 additional subjects may be enrolled for a maximum of 47 evaluable subjects across approximately 70 sites. Approximately 50% of enrolled subjects will be younger than 12 years of age to provide adequate PK data for this age subset.

If during Stage 1, at least 3 of 18 subjects achieve a morphologic complete response (either CR or CRi) within the first 4 cycles of study treatment, then the study will proceed to Stage 2; otherwise, the study will be terminated. Similarly, if at the final analysis, at least 8 of 43 evaluable subjects across Stages 1 and 2 achieve a response (CR/CRi) within the first 4 cycles of study treatment, it will be concluded that lenalidomide has sufficient activity in pediatric AML to warrant subsequent study.

Morphological response will be assessed using the modified AML International Working Group (IWG) criteria (Cheson, 2003) (Appendix D).

The OEP will allow subjects who demonstrate clinical benefit, as assessed by the Investigator at the completion of 12 cycles of lenalidomide therapy, to continue receiving oral lenalidomide until they meet the criteria for study discontinuation. In the OEP, only safety, dosing, concomitant medications/procedures, and second primary malignancies (SPMs) will be monitored (Table 2).

An external DMC will evaluate safety and treatment activity data in an ongoing and periodic manner to assess benefit-to-risk considerations throughout the study. The function of the DMC is to monitor the safety and activity of the study treatment. Once 4 subjects having received at least one dose of lenalidomide have completed at least 1 cycle of study treatment or discontinued treatment (whichever occurs first), the DMC will evaluate the safety data available and provide a recommendation. The DMC will also provide recommendations about the continuation of the study from Stage 1 to Stage 2 (continue as planned, continue with modifications or stop treatment and/or enrollment) and advise on ways to improve quality. The underlying principles for the DMC are ethical and safety aspects for the subjects. It will be the task of the DMC to examine whether the conduct of the study is still ethically justifiable, whether security of the subjects is ensured, and whether the process of the study is acceptable. For this, the DMC has to be informed about the adherence to the protocol, the subject accrual, and any observed AE(s). The composition and responsibilities of the DMC, including the structure and procedures of its meetings, will be outlined in a DMC charter.

The study consists of 3 phases: Screening Phase, Treatment Phase and Follow-up Phase.

Screening Phase

The Screening Phase will start from the time of signing the informed consent form (ICF)/informed assent form (IAF) and will last no more than 14 days, at which time the Treatment Phase will begin (Cycle 1 Day 1). Subject's screening procedures are to occur during the Screening Phase within 14 days prior to dosing on Cycle 1 Day 1.

As part of the screening procedures, a fresh bone marrow aspirate and/or a bone marrow biopsy paraffin embedded slide will be collected from all subjects for confirmation of disease. The confirmation of disease will be performed locally.

A standard cytogenetic metaphase preparation from the fresh BMA must be prepared for the cytogenetic testing/chromosome analysis including karyotype. The local site will submit the reports of the karyotype, FISH studies, as well as any available data on molecular mutations (FLT3, CEPBa, NPM1, and others including exome sequencing via Foundation Medicine or other sources) if performed, to the central reviewer at [REDACTED]. If subjects have a FISH detectable marker, the test should be repeated until CR/CRi and at relapse.

The BMA slide (and/or bone marrow biopsy embedded paraffin slide) and peripheral blood smear from screening **must** be provided to the central reviewers at [REDACTED]. The central review [REDACTED] will provide standardized analysis and reporting for all subjects. The central reviewer's assessment will be used retrospectively to confirm diagnosis.

Creatinine clearance (CLcr) will be measured at screening using [Table 4](#) (see Section 7.2).

Treatment Phase

The lenalidomide dose will be calculated based on body weight. The starting dose will be 2 mg/kg/day with a maximum dose of 70 mg/day. Subjects enrolled in the study will receive lenalidomide for the first 21 days of each 28-day treatment cycle for up to a maximum of 12 cycles of study treatment. After the completion of 12 cycles of study treatment, subjects who demonstrate clinical benefit as per the Investigator may continue to receive lenalidomide in an OEP ([Appendix L](#)) until they meet the criteria for study discontinuation.

In the event of a specific protocol-defined toxicity, no more than 2 dose reductions will be allowed to doses of 1.4 mg/kg/day (not exceeding 50 mg/day) and 1 mg/kg/day (not exceeding 35 mg/day). The dose will not be re-escalated once it has been reduced ([Table 6](#)). Subjects who do not tolerate the minimum dose level of 1 mg/kg/day (not exceeding 35 mg/day) will be discontinued from the study. For additional details regarding dose reductions and dose capping see Section 8.2.1.

During the Treatment Phase, subjects will be assessed for treatment activity based on modified IWG AML Response Criteria ([Appendix D](#)). To determine morphologic CR/CRi, BMA/biopsy and peripheral blood smear must be collected from all subjects at the completion of the 21-day treatment period of the predefined treatment Cycles 1, 2, 3 and 4 within 6 days **before dosing for each subsequent cycle** (ie, between Day 22 to Day 27 of that cycle) ([Table 2](#)). If morphologic CR/CRi is achieved within the first 2 cycles, BMA/biopsy and peripheral blood smear will not be required at the end of Cycle 3. For all subjects, BMA/biopsy and peripheral blood smear must be performed at the completion of Cycle 4, and at the Treatment Discontinuation Visit or at the time of suspected relapse (whichever occurs first). For subjects who are assessed as having partial response, the BMA/biopsy and peripheral blood smear will be repeated at Cycle 8 unless the subject goes to allogeneic HSCT, and at the Treatment Discontinuation Visit or at the time of suspected treatment failure (whichever occurs first). **A bone marrow biopsy is required only if a bone marrow aspirate cannot be obtained.** Subjects demonstrating clinical benefit as per the Investigator at the end of Cycle 4 and beyond may continue to receive lenalidomide on study for up to 12 cycles in the absence of protocol-defined toxicity or transitioning to allogeneic HSCT.

During the study, repeat of local testing of bone marrow cytogenetics and FISH for any positive markers is to be completed whenever a BMA/biopsy is obtained. However, if the cytogenetics/FISH results are 'normal' at screening or at any point during the study, cytogenetic analysis is not required to be repeated except at the Treatment Discontinuation Visit or at the time of bone marrow evaluation for suspected relapse (whichever occurs first).

In order to establish lenalidomide plasma PK parameters in subjects with rrAML, blood samples will be collected at specified time points ([Table 3](#)) for up to 24 hours postdose from all enrolled subjects during Cycle 1 Day 1 (Instructions for PK sample handling are in [Appendix H](#)).

Dose interruptions, delays and modifications may be required to manage adverse events (AEs) during study treatment (see [Section 8.2.1](#) for details). In order to optimally benefit from protocol-prescribed therapy, the Investigator should aim to treat subjects for **at least 4 cycles** with lenalidomide. Subjects demonstrating clinical benefit as per the Investigator at the end of Cycle 4 and beyond may continue to receive lenalidomide on study up to 12 cycles in the absence of protocol-defined toxicity or transitioning to allogeneic HSCT. Subjects may be

treated beyond 12 cycles of study treatment in the OEP if they continue to benefit and have not undergone HSCT.

Subjects may be discontinued from the treatment at the Investigator's discretion for any of the reasons as detailed in Section 12. All discontinued subjects, regardless of reason for discontinuation, should undergo treatment discontinuation procedures at the time of investigational product (IP) discontinuation (Table 2). The reason for discontinuation will be recorded in the electronic case report form (CRF) and in the source document.

An interim analysis is planned to take place once the first 18 subjects evaluable for the primary endpoint have been accrued and completed up to 4 cycles of lenalidomide treatment if they have not stopped therapy before 4 cycles. The interim analysis will assess the number of subjects with CR or CRi under lenalidomide treatment.

Follow-up Phase

Subjects will enter the Follow-up Phase at the time of permanent discontinuation of IP and will be followed for up to 5 years from the last subject's first dose, unless the subject dies, withdraws consent or is lost to follow-up. The Follow-up Phase may not be terminated because of new anticancer treatment or HSCT.

The 28-day Follow-up Visit will occur 28 days after the subject's last dose of IP. At this visit, subjects will be monitored for the collection of AEs and concomitant medications/procedures used to treat the AEs. Female Children of Childbearing Potential (FCCBP) and Females of Childbearing Potential (FCBP) will have a pregnancy test at the 28-day Follow-up Visit (see Section 6.8 and Section 7.2).

[figure not shown]
After the 28-day Follow-up Visit, subjects will be followed up by phone or clinic visit, whichever is the institution's normal standard of care, every 3 months for a maximum of 5 years from the last subject's first dose, regardless of new anticancer treatment or HSCT, for SPMs, safety issues (any drug-related SAEs), and start of new anticancer therapies.

Optional Extension Phase

Upon completion of 12 cycles of lenalidomide therapy per protocol, subjects who are demonstrating clinical benefit as assessed by the Investigator and who do not meet any of the criteria for treatment discontinuation (see Section 12) may enter the optional extension phase (OEP).

Details for the OEP are provided in Appendix L.

Figure 1: Overall Study Design

AML = Acute Myeloid Leukemia; HSCT = Hematopoietic Stem Cell Transplant; IAF = Informed Assent Form; ICF = Informed Consent Form; [redacted]; Max = Maximum; [redacted]; SAE = Serious Adverse Event

^a If 3 or more subjects in Stage 1 achieve a morphologic complete response (either complete response or complete response with incomplete blood count recovery) within the first 4 cycles, the study will proceed to Stage 2.

